#### **Informed Consent:**

Exception from Informed Consent will not be used in this trial. Written informed consent will be obtained from potential subjects or a legally authorized representative prior to randomization.

**Randomization:** Randomization will occur once the informed consent has been obtained. A 1:1 allocation will be used for the randomization. Subjects will be randomized to either the intervention arm (use of plasma) or the control arm (standard of care). Randomization will be performed using a computer-generated random sequence placed in opaque, consecutively-numbered, sealed envelopes kept in the locked Center for Translational Injury Research (CeTIR) office. A CeTIR research coordinator is available 24 hours a day, 7 days a week. Allocation will be 1:1. Patients will be stratified by enrollment location (STICU, ED, and Medical) in 5 blocks of 4 and 1 block of 6 for a total of 26 patients. **[Figure 4].**

**Figure 4** – Flow diagram depicting patient screening, enrollment, and randomization.

**Intervention:** Initial resuscitation with plasma will be 10 mL/kg (700 mL in a typical 70 kg adult). Traditional doses of plasma, when used to correct coagulopathy range from 10-15 mL/kg. The plasma will be administered at a rate of 2-3 mL/kg/hr (140-210 mL/hr in a typical 70 kg adult). A research physician will be at bedside to follow patient resuscitation. Plasma administration may be terminated before the entire dose is administered if patients show clinical improvement, or if the treating clinician has concerns about circulatory overload. After the initial dose of plasma has

been given, subsequent fluid resuscitation (crystalloid or colloid) will be given at the discretion of the treating clinician.

The blood bank will have thawed plasma available on call as soon as an eligible patient has been identified. Type and screen will be performed concurrently to provide donor-matched plasma for subjects randomized to intervention group. For patients who proceed to the operating room during fluid resuscitation, the anesthesiology team will continue fluid administration per study protocol.

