**Control:** Usual care using balanced crystalloids (Iso-Lyte or Plasma-Lyte) only will follow Surviving Sepsis Campaign guidelines. Controls will receive 30 mL/kg (2100 mL in a typical 70 kg adult) of crystalloids within the first 3 hours. Crystalloid administration may be terminated before the entire dose has been administered if patients show clinical improvement, or if the treating clinician has concerns about circulatory overload. After the initial dose of crystalloids has been given, subsequent fluid resuscitation (crystalloid or colloid) will be given at the discretion of the treating clinician.

**Observational Arm:** Patients with suspected sepsis who do not meet the criteria for randomization or unable to obtain informed consent in a timely fashion (within 3 hours of research team being notified) will be enrolled in a prospective observational arm of the study. Baseline demographic and hospitalization data including the fluid therapy per the attending physician's discretion will be collected. Blood samples will also be collected at 0, 2, 3, 6, 12, and 24 hours upon determination of patients' eligibility for the observational study arm. A waiver of informed consent will be requested given that no intervention will be performed on the patient and that the study will be at minimal risk to the patient. The research team will attempt to obtain written informed consent from the patient or his/her legal authorized representative for 24 hours after patient enrollment into the observational study arm. If informed consent is denied by the patient or his/her legal authorized representative, no further data or blood samples will be collected and any data or blood samples collected prior to decline of participation will not be used in this study.

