	T = 0	T = 2	T = EoR	T = 6	T = 12	T = 24
Serum Biomarkers	✓	✓	✓	✓	✓	✓

Serum biomarkers = syndecan-1, sTM, sFLT-1, VEGF, sRAGE, HMGB-1, IL-6, 8, 10, 1 $\alpha$ , 1 $\beta$ , vWF, tPA, NE, and epinephrine;  
EoR = End of Resuscitation (variable, depending on patient response to fluids)

resuscitation, time on vasopressors, time until lactate normalization, ventilator days, ICU-free days, and hospital length of stay. Organ dysfunction will be measured including acute lung injury and acute renal failure. Standardized definitions will be used as outlined in the method of operation used in previously conducted trials by our group. Potential harms of plasma administration will be assessed including symptomatic and asymptomatic venous thromboembolisms, transfusion-related allergic reactions, febrile non-hemolytic transfusion reaction, delayed-serological transfusion reactions, and transfusion-associated circulatory overload. Risk/safety evaluation will be performed at half recruitment (13 randomized patients).

**Blinding:** The healthcare provider will not be able to be blinded to the study intervention. The outcome assessors will be blinded when feasible, and the laboratory technicians and statisticians will be blinded.

**Sample Size:** We propose to enroll 26 patients (13 in each treatment arm) for the pilot randomized study to obtain unbiased estimates of treatment effect. We propose to enroll up to 100 patients to the observational study arm. Because this is a feasibility pilot study, we do not provide a power analysis for any outcomes since no formal hypothesis testing will be conducted. Instead, we will calculate estimates of treatment effect and 95% confidence intervals for all measures. We will also calculate probabilities of treatment benefit/harm using Bayesian analyses and conservative neutral priors. These estimates will inform the design of a future larger trial.

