**Statistical Analysis:** Because this is a pilot, efficacy trial, we will perform both a per-protocol and an intention-to-treat analysis. Both frequentist and Bayesian analysis will be performed. For the primary outcome and all continuous outcomes (using variable transformations if needed), we will use mixed models that include group and time period as covariates with a random subject effect. We will report group differences and 95% CIs from these models. For binary outcomes, a log binomial (or Poisson in case of non-convergence) will be used to estimate relative risks and 95% CIs. Hazard ratios and 95% CIs will be reported for time-to-event comparisons. For the Bayesian analysis, neutral conservative priors (that exclude large treatment effects almost never seen with medical interventions) will be used to estimate the probability of both benefits and harms, as defined by our primary and secondary outcomes.

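### Circulatory overload is recorded only when transfusion-associated, so a control patient can count only after a blood product and any between-arm overload estimate is tilted against plasma

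*Combined protocol and SAP*

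**What the plan says.** The outcomes text opens its safety list with "Potential harms of plasma administration will be assessed including symptomatic and asymptomatic venous thromboembolisms", goes on to transfusion reactions, and closes with "delayed-serological transfusion reactions, and transfusion-associated circulatory overload". The documents name no other overload outcome. The complications in Appendix A include ARDS, AKI, thromboembolic events and transfusion reactions, but neither circulatory overload nor pulmonary edema. Appendix A does collect pretibial edema and the fluids given, and the outcomes text measures acute lung injury. None of these is designated as a measure of overload.

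The Intervention and Control paragraphs each give the same ground for ending the study fluid early: "if the treating clinician has concerns about circulatory overload". The plasma dose is 10 mL/kg, and "The plasma will be administered at a rate of 2-3 mL/kg/hr". In the other arm, "Controls will receive 30 mL/kg (2100 mL in a typical 70 kg adult) of crystalloids within the first 3 hours". Later fluid is discretionary in both arms. The Co-interventions paragraph provides red cells for low hemoglobin in both groups.

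Specific Aim 3 asks for the effect of plasma on adverse events. The Sample Size paragraph commits to effect estimates with 95% confidence intervals for every measure, to inform a larger trial. The Statistical Analysis paragraph adds relative risks for binary outcomes and a Bayesian analysis to "estimate the probability of both benefits and harms, as defined by our primary and secondary outcomes".

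**The concern.** The protocol accepts that either fluid may overload a patient, but the only overload event it defines requires a transfusion. Every patient who starts plasma meets that precondition through the assigned treatment. A control meets it only by being given a blood product for another reason. The same clinical picture can therefore count in one arm and not in the other.

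This bears on a question the trial itself raises. The Background cites observational data linking more early fluid to higher mortality, and fewer edema-related complications with plasma in trauma. The Preliminary Data report less total fluid and lower lung wet-to-dry ratios with plasma in rats. Less overload with plasma is thus a plausible benefit, and the present definition could show it as a harm. The half-enrollment safety review, at 13 randomized patients, would see the same asymmetry with about six or seven patients per arm.

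**Working it through.** **The plan's own figures.** 10 mL/kg × 70 kg = 700 mL and 30 mL/kg × 70 kg = 2100 mL, as stated. The planned initial volumes are in the ratio 2100/700 = 3.0. Over the first 3 hours the plasma rate delivers 2 × 3 = 6 to 3 × 3 = 9 mL/kg, against 30 mL/kg in controls. The plan has 13 patients per arm and gives no event rates.

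**Assumptions for the illustration.** None of these comes from the documents.
- p: true overload risk, the same in both arms; 20% is used where a value is needed.
- t: share of controls given a blood product, 10%, 20% or 30%, taken as unrelated to overload risk. All overload in these controls is counted.
- a: share of plasma-arm overload classed as transfusion-associated, first set to 1.

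**Recorded relative risk.** The recorded risk is p × a with plasma and p × t in controls, so the recorded relative risk is the true relative risk × a/t.
- Equal true risk, a = 1: 1/0.10 = 10, 1/0.20 = 5, 1/0.30 = 3.3. The truth is 1.
- Equal true risk, a = 0.5: 0.5/0.10 = 5, 0.5/0.20 = 2.5, 0.5/0.30 = 1.7.
- Control risk twice the plasma risk (true relative risk 0.5), a = 1: 0.5/0.10 = 5, 0.5/0.20 = 2.5, 0.5/0.30 = 1.7. The direction reverses.
- The same true relative risk of 0.5 with a = 0.5 and t = 0.30: 0.5 × 0.5/0.30 = 0.83. The difference is largely hidden.

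In this set-up the tilt disappears only if t is as large as a.

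**Counts at p = 20%, a = 1.** Expected plasma events are 13 × 0.20 = 2.6. Expected recorded control events are 13 × 0.20 × t = 0.26, 0.52 and 0.78. The chance of no recorded control event together with at least one plasma event is (1 − 0.20t)^13 × (1 − 0.80^13):
- t = 10%: 0.769 × 0.945 = 73%
- t = 20%: 0.588 × 0.945 = 56%
- t = 30%: 0.447 × 0.945 = 42%

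With one definition applied to both arms, expected events are 2.6 in each, the true relative risk is 1, and the same chance is 0.80^13 × (1 − 0.80^13) = 0.055 × 0.945 = 5%.

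**The case against.** The strongest reply is that this is a safety list for a blood product. It is open-ended, its items are known reactions to that product, and it does not announce overload as a between-arm contrast. The Bayesian sentence can be read as concerning the direction of effect on the listed outcomes. That is fair as far as it goes. But Aim 3 seeks an effect on adverse events, and the Sample Size paragraph promises estimates for every measure, so a comparison is the natural result of following the plan.

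The definitions also cannot be fully checked. They are deferred to the manual of operations of earlier trials, and the opening of the secondary-outcome text is missing from the available copy. An arm-neutral definition may exist there. What can be read names only the transfusion-associated event.

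The consequences of crystalloid overload are not invisible. Total 24-hour fluid, acute lung injury, ARDS, ventilator days and pretibial edema are collected in both arms. This limits the loss but supplies no overload outcome.

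The threefold ratio is for the planned initial dose only. Crystalloid before randomization (under 30 mL/kg), early stopping and later fluid all vary. The planned difference of 1400 mL is 1400/8000 = 18% to 1400/6000 = 23% of the 6 to 8 L per day that the protocol cites. This stands.

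Sparse cells come with 13 patients per arm. At a 10% risk, even a common definition gives no control events with probability 0.90^13 = 25%. The Bayesian analysis does not fail at a zero cell. Both points are right, but a neutral prior only shrinks an estimate and does not restore events that were never counted.

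**Conclusion.** The point holds: as written, overload is defined so that controls can enter the count only through a blood product, and any comparison of arms is tilted against plasma. The size is unknown. The relative risks of 10 to 3.3 are upper-end illustrations. They assume that every plasma-arm overload is classed as transfusion-associated, although those patients may also have received crystalloid before and after. They also assume that transfused controls are at no higher risk of overload than other controls.

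Three stronger readings are tempting and are not supported:
- A reader might infer that controls must score zero and that plasma must look worse whatever the truth. Red cells are provided for in both arms, and trauma and surgical patients are included, so control events are possible.
- A reader might infer that controls receive three times the fluid overall. The documents fix that ratio only for the planned initial dose.
- A reader might infer that the whole harm comparison is one-sided. Thromboembolism and organ dysfunction are recorded in both arms; the asymmetry concerns overload and the transfusion-reaction items.

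The primary biomarker outcome is unaffected, and the pilot plans no formal hypothesis test. The change should still be made, because these estimates are meant to inform the larger trial and the correction is cheap.

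**What to change.** - Define circulatory overload once, by criteria that do not refer to transfusion, and record it in both arms over the same window from T=0.
- Add it as an item to the complications in Appendix A.
- Use this outcome for the between-arm estimate and for the half-enrollment safety review.
- Report transfusion-associated overload and transfusion reactions as descriptive counts among transfused patients in either arm.
- If the external manual already has an arm-neutral definition, cite it in the outcomes text and state that it applies to both arms.

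The cost is a revised outcome sentence and one more data item. The plasma-specific reactions become descriptive and are no longer contrasted between arms. No additional imaging or staff is needed, and treatment does not change.

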### **Hypothesis and Specific Aims:**

**Hypothesis:** We hypothesize that among patients with septic shock, initial resuscitation with plasma versus balanced crystalloids will decrease biomarkers of endotheliopathy, improve patient outcomes (such as decrease number of ICU-free days, decreased morbidity associated with end-organ damage), and reduce in-hospital all-cause mortality. We propose to perform a pilot RCT to test this hypothesis using the following specific aims:

**Specific Aim 1:** To evaluate the effects of plasma versus balanced crystalloids on serum markers of glycocalyx breakdown, endothelial leakage, inflammation, hemostasis, sympathy-adrenal activation, and degree of coagulopathy (using rapid thromboelastography parameters) **[Figure 1]**.

**Specific Aim 2:** To evaluate differences in total volume of fluids needed to resuscitate patients in the plasma group versus crystalloids group during the initial 24 hours of resuscitation.

**Specific Aim 3:** To determine the effect of plasma resuscitation on organ dysfunction, ventilator-free days, intensive care unit (ICU) free days, hospital length of stay, mortality, and adverse events.

[figure not shown]

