#### **Data Collection:**

Data collected will include: demographics, past medical history, hospital information including

initial resuscitation information and post-operative care, complications (**Appendix A**), and discharge information. A list of the data elements to be collected can be found in Appendix A. Data will be collected from the subject's medical record and the trauma registry. Risk/Safety evaluation will be performed at half enrollment (at 13 enrolled and randomized patients).

All subjects enrolled in this study will be assigned a study specific number. The de-identified data will be entered into a secure, password protected database accessible to only those involved in the study. A study linking log which will link subject identifiers to the study number will be kept by the study PI.

To ensure patient confidentiality is maintained at all times, all data will be maintained in accordance with HIPAA rules and regulations. Hard copy source documentation will be kept in a secure area in a locked office and electronic data will be stored on secure, password-protected computers accessible to only those study specific personnel.

**Outcomes - Biomarkers of Endothelial and Glycocalyx Injury:** The primary outcome is a reduction in serum biomarkers associated with glycocalyx breakdown (syndecan-1, sTM), endothelial leakage (sFLT-1, VEGF, sTM), sympatho-adrenal activation (NE, epinephrine), and inflammation (VEGF, sRAGE, HMGB-1, IL-6, 8, 10, 1 $\alpha$ , 1 $\beta$ ) in the plasma group. A rodent model has shown evidence of glycocalyx restoration after 2 hours of resuscitation with plasma as compared to crystalloid. Biomarkers will be drawn at 0, 2, end of initial bolus of fluid administration, 6, 12, and 24 hours to evaluate their trend in response to plasma versus crystalloid resuscitation. Timing of biomarker lab draw at the end of the initial fluid bolus will be variable since termination of fluid resuscitation depends on patients' clinical response. Lactic acid will be drawn per standard of care to guide resuscitation. Standard labs for critically ill patients (such as complete blood count, basic metabolic panel, and arterial blood gases) will be obtained per STICU protocol. See **Table 2** for timing of biomarker lab draws. Funding for measuring biomarkers will be obtained from an additional source if the grant is awarded.

Table 2: Timing of Lab Draws Upon Randomization (T=0) in hours						

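### The primary mixed model, with the terms it names, gives one average group difference: it does not address the biomarker trend, leaves the T=0 value unused as a covariate, and does not say how T=0 enters

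*Combined protocol and SAP*

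**What the plan says.** The Statistical Analysis paragraph covers the primary outcome and all continuous outcomes in one sentence: "we will use mixed models that include group and time period as covariates with a random subject effect". It continues: "We will report group differences and 95% CIs from these models". No time point, contrast or reference value is named.

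The Outcomes paragraph on biomarkers sets the schedule and its purpose: "Biomarkers will be drawn at 0, 2, end of initial bolus of fluid administration, 6, 12, and 24 hours to evaluate their trend". It motivates early sampling with animal data: "A rodent model has shown evidence of glycocalyx restoration after 2 hours of resuscitation with plasma as compared to crystalloid". The outcome itself is worded as a fall: "The primary outcome is a reduction in serum biomarkers associated with glycocalyx breakdown". Whether that fall is measured against T=0 or against the control arm is not said.

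Table 2 places T=0 at randomization, and Screening and Enrollment has study fluid start immediately afterwards, so T=0 is a pre-treatment value. The end-of-resuscitation (EoR) draw has no fixed clock time.

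Specific Aim 1 is broader: "To evaluate the effects of plasma versus balanced crystalloids on serum markers of glycocalyx breakdown". The Sample Size paragraph says patients are enrolled "for the pilot randomized study to obtain unbiased estimates of treatment effect", and adds: "These estimates will inform the design of a future larger trial".

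**The concern.** Two things are missing between the schedule and the model.

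First, a model with main effects of group and time period assumes that the arms differ by the same amount at every draw. It cannot show when an effect appears or fades, which is what repeated draws over 24 hours can add.

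Second, every randomized patient is scheduled for a pre-treatment value, and the plan does not say what it is for. It could be an outcome row, be left out, or be subtracted to give change from baseline. All three fit the text. They can give different estimates and different intervals from the same data, and none of them uses T=0 as a covariate.

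The pilot plans no formal testing, so the estimates and their 95% CIs are its main product, and they are meant to feed the design of a larger trial. An estimate that depends on an unstated choice is a weak planning input.

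**Working it through.** **Inputs from the documents.** 13 patients per arm; draws at 0, 2, EoR, 6, 12 and 24 h; 95% CIs. The plan gives no SD, effect size or correlation, so it has no precision figure to reproduce. The sample size agrees with the blocks: 5 × 4 + 1 × 6 = 26.

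**Assumptions.** SD 1 at each draw, complete data, and equal within-patient correlation r = 0.3, 0.5 or 0.7 between any two draws (compound symmetry). AR(1) is a sensitivity case. Estimating the baseline slope from 26 patients inflates variance by f = 1 + 1/(26 − 4) = 1.0455. Every variance term below is multiplied by 2/13.

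**1. Trend.** With complete data the group coefficient is the plain mean of the per-draw differences.
- 1 SD effect at 2 h, EoR and 6 h only: 3/6 = 0.50 SD over six draws, 3/5 = 0.60 SD over five.
- 1 SD effect at 6, 12 and 24 h only: again 0.50 and 0.60 SD.

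The two courses are opposite in timing, and the model reports them as identical.

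**2. If T=0 is an outcome row.** The expected difference at T=0 is zero, so a constant post-treatment effect d is estimated as 5d/6. The SE is √[(2/13)(1+5r)/6] = 0.253, 0.300, 0.340. For d = 1 the interval is centred 1/6 SD away from d. The noncentrality is (1/6)/SE = 0.658, 0.556, 0.491, and the noncentral t on 24 df gives coverage of the true effect of 90.3, 91.7 and 92.4%.

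**3. If T=0 is dropped or subtracted.** Here the same five post-baseline draws are compared throughout, so that only the use of T=0 changes.

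| | r = 0.3 | r = 0.5 | r = 0.7 |
|---|---|---|---|
| T=0 dropped: (1+4r)/5 | 0.440 | 0.600 | 0.760 |
| Change from T=0: (1+4r)/5 + 1 − 2r | 0.840 | 0.600 | 0.360 |
| Adjusted for T=0: f[(1+4r)/5 − r²] | 0.366 | 0.366 | 0.282 |
| Variance ratio, dropped / adjusted | 1.20 | 1.64 | 2.69 |
| Variance ratio, change / adjusted | 2.30 | 1.64 | 1.28 |

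The SEs are 0.260, 0.304, 0.342 (dropped), 0.359, 0.304, 0.235 (change) and 0.237, 0.237, 0.208 (adjusted).

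Break-even for dropped against adjusted: setting (1+4r)/5 = f[(1+4r)/5 − r²] gives r ≈ 0.11. Below that, adjustment gains nothing.

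**4. AR(1) sensitivity**, adjacent correlation 0.5, 0.7, 0.9 over draw order. The variance term of the five-draw mean is 0.445, 0.616, 0.852, and its covariance with T=0 is 0.194, 0.388, 0.737. The adjusted term, f × (variance − covariance²), is 0.426, 0.486, 0.322. The dropped/adjusted ratio is 1.04, 1.27, 2.64.

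**5. Precision at a single time.** The adjusted SE is √[(2/13) f (1−r²)] = 0.383, 0.347, 0.286 SD. With t on 23 df the 95% half-width is 0.79, 0.72, 0.59 SD.

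**The case against.** The sentence says what the models include, not what they are limited to, and it speaks of differences in the plural. It also covers single-value outcomes such as hospital length of stay, which have no time period, so it cannot be a complete specification of every model. This stands. A reader might infer that the plan rules out an interaction or a baseline term; the text does not support that. It supports only that neither is stated.

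An average difference is a legitimate summary, and it can answer Aim 1 as worded. This also stands. The trend purpose in the Outcomes paragraph, however, is left without a stated analysis.

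A reader might infer that the primary estimate is biased or diluted as planned. That too goes beyond the text. The 5/6 dilution belongs to one of three possible uses of T=0. An unadjusted randomized contrast is unbiased for the average that it targets. Even with T=0 as an outcome row, the shortfall of 0.17 SD on a 1 SD effect compares with a 95% half-width of 0.52 to 0.70 SD (2.064 × 0.253 to 2.064 × 0.340). For that reading I do not set its raw SE against that of the adjusted contrast, because the two estimate different quantities.

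Finally, the precision gain depends on correlations that the documents do not give, and 13 per arm will locate a trend poorly. Both are true. The missing trend analysis and the undefined role of T=0 depend on no correlation.

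**Conclusion.** The point holds as a gap in specification with an inexpensive better method; it is not an error that invalidates the comparison. With the terms named, the primary model yields one average group difference, which cannot separate an early effect from a late one (0.50 SD in both examples over six draws, 0.60 SD over five), and it leaves a scheduled pre-treatment value unused as a covariate.

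The size of the second part depends on how T=0 is used:
- **Outcome row:** a constant effect is reported at 5/6, and coverage of a true 1 SD effect is about 90-92%.
- **Dropped:** variance is 1.20 to 2.69 times that of the adjusted five-draw average for r from 0.3 to 0.7, and 1.04 to 2.64 times under AR(1) from 0.5 to 0.9.
- **Change from T=0:** variance is 2.30 to 1.28 times that of the adjusted average over the same r.

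These figures rest on complete data, equal variances and assumed correlations. It should be fixed before analysis, because the estimates are intended for planning a later trial.

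**What to change.** State in the SAP:
- Post-baseline biomarker values, transformed as needed, are analysed in a mixed model with group, time (categorical), group-by-time, the patient's own T=0 value as covariate, and a random subject effect. A constrained longitudinal model with a common baseline mean is an alternative and keeps patients whose T=0 value is missing.
- T=0 is not a treatment-effect outcome row.
- The group difference at each post-baseline time is reported with its 95% CI, together with one average post-baseline contrast per biomarker, named in advance.
- Whether the EoR draw belongs to that average is decided in advance, and its actual draw time is used in the analysis. This matters because EoR can fall at different clock times by arm: at the stated rates a full plasma dose takes 10/3 = 3.3 h to 10/2 = 5.0 h, the control volume is planned within 3 h, and either may stop early.

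The cost is wording and about 4-5 degrees of freedom: 1 for baseline, plus 3 for group-by-time with four post-baseline draws or 4 with five. Per-time estimates will be imprecise (half-widths of 0.59 to 0.79 SD), so the average contrast should carry the main summary. At very low within-patient correlation the adjustment gains little or nothing. One data field may be needed if the EoR draw time is not already recorded.

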### **Study Design & Methods:**

The proposed trial is a pilot, efficacy, single-center RCT comparing initial plasma to balanced crystalloid resuscitation in surgical patients with septic shock. The trial will investigate modulation of SHINE as a strategy by which outcomes in shock patients may be improved. The trial will follow the Consolidated Standards in Reporting of Trials (CONSORT) guidelines and has been registered on ClinicalTrials.gov (NCT03366220).

**Setting:** The study will take place at Memorial Hermann Hospital – Texas Medical Center (MHH-TMC), a Level I trauma and tertiary care center located in Houston, Texas.

**Study population:** The target population includes critically ill (including medical patients), traumatically-injured or surgical patients who have sepsis, hypotension with MAP < 65 mmHg, and signs of hypoperfusion such as lactic acid > 2.2 mmol/L, altered mental status or decreased urine output (< 0.5 mL/kg in the past hour).

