### Hospital Information

- Admission date/time (ED and STICU/SIMU)
- Time of injury
- Type of injury
- Pre-hospital treatment (LSIs)
- Initial resuscitation therapy (blood products, IR, OR, LSIs)
- Vital signs
- Degree of pretibial edema
- Laboratory results
- Diagnostic procedure results
- Daily STICU/SIMU data ( i.e. ventilator settings, vital signs)
- Vasopressor use (medication, dose)
- Blood products and fluids
- Sepsis diagnostic information
- Operative and endovascular interventions
- Complications (ARDS, AKI, venous thromboembolic events, sepsis, severe sepsis, septic shock, transfusion reactions, infections, multi-organ failure, pneumonia)

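### The continuous clinical outcomes are compared with no baseline severity term; with 13 per arm, one prespecified covariate the trial already records would probably add precision and remove conditional error from chance imbalance

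*Combined protocol and SAP*

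**What the plan says.** The only analysis text is the Statistical Analysis paragraph. For the primary outcome and every other continuous outcome it specifies "mixed models that include group and time period as covariates", plus a random subject effect. It names no baseline severity measure, baseline value or stratification factor.

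The Sample Size paragraph states "We propose to enroll 26 patients (13 in each treatment arm"). It plans no hypothesis tests, only estimates with 95% confidence intervals and Bayesian probabilities of benefit and harm, and adds: "These estimates will inform the design of a future larger trial".

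Under Randomization, "Patients will be stratified by enrollment location (STICU, ED, and Medical"). This is the only balancing factor.

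The target population is "critically ill (including medical patients), traumatically-injured or surgical patients who have sepsis", with hypotension and signs of hypoperfusion.

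Severity information is recorded. MAP, lactate, mental status and urine output appear among the randomization criteria. The Endpoints of Resuscitation paragraph sets a lactate clearance goal, which needs a starting lactate. Appendix A (Hospital Information) lists "Laboratory results" and "Vasopressor use (medication, dose"), along with vital signs.

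**The concern.** The biomarkers are drawn at T=0, so they at least have a baseline of their own. Total 24-hour fluid volume (Aim 2), ICU-free days and hospital stay (Aim 3) do not. Each is one number per patient, so neither the time term nor the subject effect has anything to model. What remains is the raw difference between arms.

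Severity at shock onset plausibly predicts these outcomes, although the documents do not say how strongly. If it does, omitting it has two costs. The intervals are wider than they need be. And in the particular trial that is run, an ordinary chance difference in severity can look like benefit or harm. Estimation is the pilot's whole purpose and its results feed the next design, so the absence of formal testing does not make this harmless.

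**Working it through.** **Plan's own figure.** The randomization list is "in 5 blocks of 4 and 1 block of 6 for a total of 26 patients": 5 × 4 + 6 = 26, or 13 per arm. This reproduces. There is no power calculation to reproduce.

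**Inputs.** n = 13 per arm (Sample Size). The correlation r between baseline severity and outcome is not in the documents; it is an assumption and is shown over a range.

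**1. Chance imbalance.** The SE of a standardized baseline difference is √(2/13) = 0.392 SD. P(|difference| > 0.5 SD) = P(|Z| > 0.5/0.392) = P(|Z| > 1.27) = 0.20.

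This assumes unstratified randomization. If location explains a share q of severity variance and stratification works fully, the SE becomes 0.392 × √(1 − q):

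| q (assumed) | SE | P(imbalance > 0.5 SD) |
|---|---|---|
| 0 | 0.392 | 20% |
| 0.3 | 0.328 | 13% |
| 0.5 | 0.277 | 7% |

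**2. Shift in the unadjusted estimate.** Shift = r × imbalance. For a 0.5 SD imbalance it is 0.15, 0.25 or 0.35 SD at r = 0.3, 0.5 or 0.7. The unadjusted 95% CI half-width is t(0.975; 24 df) × 0.392 = 0.81 SD, so a 0.25 SD shift is 0.25/0.81 = 31% of it.

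**3. Effect on the planned Bayesian output.** With no true effect, an estimate lying at that 0.25 SD shift has z = 0.25/0.392 = 0.64. This gives a probability of benefit (or harm) of about 74% under a flat prior and about 69% under a neutral normal prior of SD 0.5 (assumption), where 50% is neutral.

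**4. Precision gained by one covariate.** Relative to the unadjusted variance, the expected adjusted variance is (1 − r²) × (1 + 1/22) = (1 − r²) × 23/22. The second factor is the cost of estimating the slope from 26 patients.

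| r (assumed) | 1 − r² | × 23/22 | Variance cut | 26 / factor |
|---|---|---|---|---|
| 0.4 | 0.84 | 0.878 | 12% | 30 |
| 0.5 | 0.75 | 0.784 | 22% | 33 |
| 0.6 | 0.64 | 0.669 | 33% | 39 |

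Break-even is at 1 − r² = 22/23, so r = √(1/23) = 0.21. At r = 0 the loss is 1/22 = 4.5% of variance.

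**5. Behaviour over trials.** This was simulated with 40,000 null trials for each of r = 0.3, 0.5 and 0.7. Over all trials, unadjusted 95% intervals cover 95%. In trials with an imbalance of at least 0.5 SD, unadjusted coverage is 93%, 89% and 85%, and adjustment restores about 95%. In those trials the mean false shift, taken in the direction of the imbalance, falls from 0.20, 0.34 and 0.47 SD to within 0.01 of zero.

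**The case against.** The strongest reply is that nothing here is invalid. The plan promises unbiased estimates with intervals, and the unadjusted analysis delivers them, because its intervals already allow for chance imbalance. A reader might infer systematic bias, or that an imbalance passes undiluted into the estimate. Neither is supported: overall coverage is 95% and only the fraction r carries through. This stands, and it limits the point to precision and to error conditional on the imbalance that occurs.

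Second, stratifying by location may balance some of the difference between medical, emergency and surgical or trauma patients. This also stands. Step 1 shows its possible size, but location is not a severity measure and is not in the model.

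Third, a reader might infer that every clinical interval is wider without the covariate. That fails below r of about 0.21. The in-hospital mortality range in the Background (12-40%) implies about 3 to 10 deaths among 26. Early deaths among the sickest would shorten stays, so r for hospital stay could be low.

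Fourth, a reader might take Appendix A as enough for a SOFA score at T=0. The documents do not show this. They name no liver test, coma scale or baseline time point, and ventilator settings are listed as daily data. A simpler single measure is the safer choice.

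Fifth, the neutral priors already restrain large chance effects. They do so only in part: in step 3 the probability falls from 74% to 69%, not to 50%.

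**Conclusion.** The point holds as an inexpensive improvement and not as a flaw in validity. For the once-measured continuous clinical outcomes, the plan has no prognostic term although usable measures are recorded. The chance of an imbalance above 0.5 SD is about 20% without any help from stratification, and at an assumed r of 0.5 a 0.5 SD imbalance moves the estimate by 0.25 SD. One covariate would cut expected variance by about 12% to 33% for assumed r of 0.4 to 0.6.

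The size rests on r, which the documents do not give, and on a roughly linear relation after any transformation. Intervals would remain wide either way: at r = 0.5 the half-width falls from 0.81 to 0.72 SD. The point does not extend to the sparse binary outcomes, where an added covariate may be unstable with so few events, and it is not a criticism of the primary biomarker analysis.

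**What to change.** Before treatment-arm data are examined, add to the Statistical Analysis paragraph that the models for 24-hour fluid volume, ICU-free days and hospital stay will include one named baseline severity covariate, defined as the last value before study fluid.

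- **Choice of covariate.** Lactate is a candidate because the clearance goal needs a starting value. MAP at randomization is another, although the entry criterion may restrict its range and so lower r. Check completeness on data pooled over arms, then fix one. Use SOFA only if its components prove complete at T=0.
- **Reporting.** Show the unadjusted estimate and 95% CI beside the adjusted one.
- **Binary outcomes.** Leave them unadjusted.
- **Missing values.** State a rule in advance that does not use outcome or arm, for example the pooled mean.

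The cost is one degree of freedom (23 instead of 24), a short derivation rule, and an expected variance increase of up to 4.5% if the covariate turns out not to be prognostic. No new data item is needed for lactate or MAP, but the time of the value used must be captured.
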